3. Client's (qualitative) views on individual therapy sessions assessed with the Helpful Aspects of Therapy form (HAT; Lewlyn, Elliott, Shapiro, Firth, & Hardy, 1988). Completed by therapist in discussion with participant.

Fidelity measure

1. Adherence to ACT related processes assessed with the ACT Fidelity Measure (ACT-FM; O'Neill, Latchford, McCracken & Graham, 2019). Completed by therapist and secondary researcher.

EXPLORATORY OUTCOMES

Adaptations made to treatment will be recorded so that commentary can be made on what adaptations to ACT may be beneficial for older adult clients. **Consideration of the impact that delivering the intervention in a remote manner will also be made and any adaptations that were made to facilitate this.**

TABLE OF OUTCOMES

Objectives	Outcome Measures	Timepoint(s) of evaluation of this outcome measure (if applicable)
Primary Objectives	1. Quality of life (OPQOL-brief).	1. Baselines, pre-, mid- and post-intervention, and at six-week follow up.
Secondary Objectives	Symptom measures 1. Cognitive functioning (MoCA). 2. Changes in levels of anxiety and depression (HADS).	1. At initial contact, by service as standard practice. 2. At initial contact, by service as standard practice. Baselines, pre-, mid- and post-intervention,

		and at six-week follow up.
	Change measures 
 1. Client's goals (PQ). 2. Client's view on change (Change Interview). 	
 1. Prior to each weekly treatment session. 2. One week after finishing treatment.
	Process measure 
 1. Psychological flexibility (CompACT-8). 	
 1. Baselines, pre-, mid- and post-intervention, and at six-week follow up.
	Session measures 
 1. Quality of life/general outcomes (ORS). 2. Therapeutic alliance (SRS). 3. Client's views on the therapy session (HAT). 	
 1-3. At the end of each weekly treatment session.
	Fidelity measures 
 1. Fidelity of treatment (ACT-FM). 	
 1. At the end of each session (by therapist) and random sampling of all sessions (by Secondary Research Supervisor).

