Up to 12 therapeutic sessions will be offered, delivered by the student researcher/therapist. At session 1 (week 4), confidentiality will be reiterated, including under what circumstances confidentiality would be broken (risk to them or others). They will also be explained the procedure of clinical supervision from [name] as well as ACT-supervision from [name] (the latter supervision not using confidential information). Participants will then be supported to complete the Simplified Personal Questionnaire (SPQ), noting their expectations for therapy, the main problems they are bothered with and duration of these. Participants will then be introduced to the underlying concepts of ACT, before starting with the proposed ACT-protocol (adapted from Petkus & Wetherell, 2013):

ACT area	Sessions and content
Values	Sessions 1-3 1. Regaining contact with values: What matters? 2. The role of religion 3. Making the most of the remaining time
Acceptance/Willingness	Sessions 4-5

	
 1. What's worked? What hasn't? What are the costs? 2. Control is the problem 3. Experiencing vs. avoiding 4. How does this fit with values?
Defusion	
Sessions 6-7
 
 1. Awareness of internal experiences 2. A thought is just a thought 3. Having a thought vs. content of a thought 4. Defusion from damaged conceptualized self
Mindfulness and Self as Context	
Sessions 8-9 (Mindfulness exercise conducted at the beginning of every session)
 
 1. Being in the present moment 2. Not judging thoughts or feelings 3. Thoughts and selves
Committed Action	
Begins during the Values sessions and continues throughout the intervention, but is emphasized during Sessions 10-12
 
 1. What goals are consistent with values? 2. What actions work toward these goals? 3. Breaking it down into steps 4. Problem-solving potential barriers 5. Enlisting support
Therapeutic blueprint	
Session 12
 
 1. Summary of the content 2. Review of SPQ and any change experienced 3. Next steps and further support options

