Therapy will use the above protocol as a guide for treatment; however, duration and content will be adapted based on the individual. Primarily this will be using extra sessions to focus on any content that participants may need further work with, but could also include a break in the middle of sessions. Sessions will predominantly be weekly and one hour in length, dependent on any required adaptations. Sessions will be delivered either over telephone or via QHealth. As ACT is a processes-based therapy, rather than a single manualised procedural treatment, adherence to a strict protocol is not theoretically mandated (Hayes & Hoffmann, 2017).

The basic structure of each session will be:

1. Participant completes weekly Personal Questionnaire before session.
2. Session begins with a mindfulness exercise.
3. Homework and concepts from previous session are reviewed.
4. New material for the session is covered.
5. Homework is assigned.
6. Therapist completed HAT with participant.
7. Participant is supported to complete ORS and SRS.

Following each session, the student researcher will receive clinical supervision with [name] by (secure) videocall or telephone to discuss any relevant case information, such as

risk and progress. A clinical note will be made on the participant's electronic case record, as in standard practice. The student researcher will also receive regular ACT supervision from [name], Secondary Research Supervisor/Chief Investigator to address any modality specific questions or dilemmas. Relevant discussions from this will be added to the participant's electronic case record as required.

At mid-point in therapy (usually session six), QP1.1 will be repeated at the start of the therapy session. QP1.1 will also be repeated at the final therapy session to act as the post-therapy time point.

During the final session, the PQ will be re-administered to determine whether there has been any change in their problem areas. Participants will also be given the opportunity to 're-author' their problem areas. This is to capture any theoretical change they may have occurred in identifying where problems at situation, as would be posited by the ACT theoretical framework (living with problems, rather than eliminating them). Participants will complete any required session questionnaires prior to filing in the PQ.

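### Change in problem areas is read from a Personal Questionnaire taken after the content of the final session, with items open to rewriting, whereas earlier ratings come before session content

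*Combined protocol and SAP*

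**What the plan says.** The Table of Outcomes gives the PQ time point as "Prior to each weekly treatment session". The list of steps for every session, under Therapeutic sessions, begins with "Participant completes weekly Personal Questionnaire before session". Neither place exempts the last session.

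Later in the same section a separate rule covers the end of therapy: "During the final session, the PQ will be re-administered to determine whether there has been any change in their problem areas". Two sentences qualify it: "Participants will also be given the opportunity to 're-author' their problem areas" and "Participants will complete any required session questionnaires prior to filing in the PQ". The Table of Outcomes times the session measures (ORS, SRS and HAT) as "At the end of each weekly treatment session". The ACT protocol table lists "Review of SPQ and any change experienced" among the contents of session 12.

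For the first administration, the session 1 text says: "Participants will then be supported to complete the Simplified Personal Questionnaire (SPQ), noting their expectations for therapy". This comes after confidentiality and supervision have been explained and before the ACT concepts are introduced.

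Table 1 uses the questionnaire, there called SPQ, in area 3 (covariation of process and weekly problems) and area 5 (event-shift sequences). The abbreviations PQ and SPQ refer to the same instrument.

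**The concern.** A repeated measure supports statements about change only if it is taken in the same way each time. Here the last value is collected at a different moment from the values before it, and the items may be altered on the same occasion. A difference between the last point and the others then mixes change in the client with change in the conditions of measurement.

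Areas 3 and 5 are two of the five kinds of direct evidence for the affirmative brief, and evidence in two areas is enough to send a case to adjudication. Each client contributes a short series that is analysed by correlation (areas 3 and 5) and visual inspection (area 5), so one point can matter. The plan guards against a wish to please elsewhere: Table 2 lists relational artefacts, and the Change Interview is given to someone the participant has not met. No comparable step is described for the final PQ.

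Rewriting raises a separate matter. Its stated aim is to capture a shift in where the client locates the problem. That is a different quantity from movement on a fixed set of items.

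**Working it through.** The plan gives no figure for this point and no PQ scale or variability, so the check sets the passages side by side.

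**Timing, assuming all 12 sessions are used**

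| Occasion | Number of ratings | When rated | Source |
|---|---|---|---|
| Session 1 | 1 | Inside the session, before ACT content | Therapeutic sessions, session 1 text |
| Sessions 2-11 | 10 | Before the session | Table of Outcomes; session steps |
| Final session, weekly rule | 1 | Before the session | Same two places, no exemption |
| Final session, re-administration | 1 | Inside the session, after the session questionnaires | Therapeutic sessions, final-session text |

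The total is 1 + 10 + 1 + 1 = 13 ratings if both final ones are taken, and 12 if only one is. The plan does not say which final rating enters the analysis, or whether the session-1 items are scored before any rewriting. Up to 12 sessions are offered, so the final session may come earlier.

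**What each choice of final score compares**

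Let P be the level that a pre-session rating would record, s any effect of completing the form inside a session, and c any effect of having just gone through the session's content. Both s and c are unknown and may have either sign. Write 1 for session 1, F for the final session and F-1 for the one before it.

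- First rating: P1 + s
- Weekly rating at session k: Pk
- Final in-session rating: PF + s + c
- Final pre-session rating: PF

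The differences are:

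- In-session final minus first: (PF + s + c) - (P1 + s) = (PF - P1) + c
- Pre-session final minus first: PF - (P1 + s) = (PF - P1) - s
- In-session final minus preceding week: (PF + s + c) - P(F-1) = (PF - P(F-1)) + s + c
- Pre-session final minus preceding week: PF - P(F-1)

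Against the weekly series, the pre-session rating removes the mismatch entirely. Against session 1, it replaces c with -s, so it is the closer match when s is smaller in size than c. The documents do not measure either. The protocol describes therapist guidance for the PQ in general, so support as such does not set the in-session ratings apart, which makes s the lesser worry.

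**Order relative to the HAT (area 5)**

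A weekly PQ rated before session k follows the HAT of session k-1, usually by about a week, and precedes the HAT of session k. The final in-session PQ follows the HAT of its own session on the same day. Area 5 asks whether events come before shifts, so the lag between event and rating also changes at the last point.

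**The case against.** The strongest reply is that the first and last PQs are both completed inside a session with support, so a first-to-last comparison is like with like, and a pre-session final score would create a mismatch. Part of this stands. It is wrong to say that every PQ other than the final one is rated before a session. But the session-1 form precedes ACT content, while the final form follows the closing session's content. The in-session final rating also stays out of line with sessions 2-11.

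A reader might infer several stronger things that the documents do not support:

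- **That the final PQ decides whether the client changed.** It addresses problem areas only. The primary outcome is the OPQOL-brief, and the panel judges overall change on the whole case material.
- **That the final rating is biased in favour of the therapy.** This is possible, but nothing in the documents shows its direction or size.
- **That the rating follows a review of change.** The review is listed as session 12 content without an order, and may be the re-administration itself.
- **That therapist involvement is peculiar to the last rating.** It is stated for the instrument in general.
- **That the pre-session rating is dropped, or that rewritten items are scored.** The plan says neither. Re-administration is compatible with both ratings being taken, and rewriting has its own stated purpose.

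What remains is more than silence. The final-session text sets a rule for determining change, and that rule sits beside a different timing rule for the same instrument.

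**Conclusion.** The point holds in a limited form. The rating assigned to determine change in problem areas is taken after the content of the final session, with items open to rewriting. The ten ratings at sessions 2-11 of a full course precede the session, and the session-1 rating precedes ACT content. This may affect the last point of the series in Table 1, areas 3 and 5. Size and direction cannot be computed from the documents.

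The conclusion rests on two readings. First, PQ and SPQ are one instrument. Second, the session questionnaires that precede the final PQ are the ORS, SRS and HAT, which the Table of Outcomes groups as session measures at the end of each session. If the phrase meant other forms given earlier in that session, the final PQ could fall sooner, but it would still be in-session and the two timing rules would still need reconciling.

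For a secondary measure in a series of up to four clients, this is a cheap improvement.

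**What to change.** Reconcile the Table of Outcomes and the session steps with the final-session text, and add wording to this effect:

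1. The post-therapy PQ score is the set of session-1 items, unaltered, rated before the final session starts, whichever session that is. This score is used in change scores, correlations and plots.
2. The in-session re-administration and any rewritten items are kept separately as descriptive material in the rich case record and do not enter those analyses.

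The cost is two or three sentences and no new data collection, because the rule for each session already calls for a rating before the last one. The small downside is that the quantitative PQ score omits any effect of the final session itself. That effect would appear only in the descriptive material, since the Table of Outcomes gives no PQ at follow-up.
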